14.3.10 EFFICACY ANALYSES

Treatment response will be assessed by RECIST v1.1 criteria for patients in the FAS at the end of Cycles 2, 4, and 6, at the 6-month, 9-month, and 12-month follow-up visits, and at the End of Study or Early Termination. Along with CR, PR and SD, the ORR will be defined as the relative frequency of patients with either CR or PR, and the DCR will be defined as the relative frequency of patients with CR, PR, or SD.

The ORR, the DCR, and the frequencies of CR, PR, SD, and PD will be summarized at the end of Cycles 2, 4 and 6 and at the 6-month, 9-month, 12-month and up to 18-month follow-up visits. A summary will also be provided of best response on study.

At the assessment at the end of Cycle 6, a one-sided exact binomial test will be used to test the null hypothesis that the ORR is no greater than 0.20 (20%) against the alternative hypothesis that the ORR is greater than 0.20 at an approximate level $p = 0.025$. A similar test against the performance level of 0.20 will be performed for the rate of best objective response on study.

Overall survival will be defined as the time in months from initial treatment until death or censoring. Patients not known to have died at the time of analysis will be censored at the time of last contact with study personnel., including patients who are lost to follow-up. The overall survival curve will be estimated for the FAS by the Kaplan-Meier method.

Progression-free survival will be defined as the time in months from initial treatment until death, disease progression, or censoring. Patients who are lost to follow-up will be censored at the time of their last contact with study personnel. Patients who leave the study to begin an alternative therapy will be censored on their day of study discontinuation. The PFS curve will be estimated for the FAS by the Kaplan-Meier method.

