	
replaced in the Monotherapy period, in Cycle 1 or 2, the number of patients will be higher than 34.
 
Analysis sets:
 
There will be two analysis sets
 
• Safety Set: All patients treated with at least one dose of idronoxil will be included in the Safety Set (SS). All analyses of safety, toxicity, and PK will be performed for this set.• Full Analysis Set (FAS): All patients who completed at least one cycle of combination therapy (at any NOX66 dose). 
Analyses of efficacy, tolerability, and biomarkers will be performed for the FAS. Separate summaries may be provided for patients participating in the Dose Escalation and Dose Expansion parts.
 
Safety (Primary analysis):
 
The safety profile will be based on Serious Adverse Events (SAEs), Treatment Emergent Adverse Events (TEAEs), standard clinical laboratory parameters (clinical chemistry, hematology, urinalysis), vital signs measurements, ECG parameters, and physical examination findings.
 
Adverse events (AE) will be coded using the Medical Dictionary for Regulatory Activities and summarized by dose when NOX66 is given alone or in combination with doxorubicin. The number and percentage of patients reporting TEAEs will be calculated overall, by system organ class, and by preferred term for each dose level. Adverse events will also be graded for severity according to the National Cancer Institute Common Terminology Criteria for Adverse Events, Version 5.0.
 
Serious Adverse Events (SAEs) will be summarized separately.
 
Cardiac AEs (including clinically significant abnormalities in ECG rhythm and waveform morphology reported as TEAEs) and changes in echocardiographic parameters will be summarized.
 
Descriptive statistics will be provided for demographics, baseline characteristics, and exposure to treatment by cohort.
 
Univariate summary statistics will be provided by dose group at each visit for quantitative laboratory parameters and vital signs and for the change from baseline in these parameters. For laboratory values and vital signs with defined CTC grades, shift tables will be provided for CTC grades from baseline to end of study and from baseline to worst value on study.
 
Univariate summary statistics will be presented for ECG parameters for the value at each measurement time point and the change from baseline to each measurement time point. A similar analysis will be provided for the worst value of each ECG parameter on study.
 
Findings from physical examinations and ECOG performance status will be summarized by dose of NOX66 given alone or in combination with doxorubicin.
 
Pharmacokinetics (Secondary analysis):
 
Individual blood concentration-time data and blood PK parameters will be summarized using descriptive statistics by dose and sampling time for idronoxil and metabolites. Separate summaries will be provided for PK

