--	--

	
samples collected for single-dose administration, repeated administration, and administration in combination with doxorubicin.
 
Blood PK parameters will be determined by noncompartmental analysis for idronoxil and metabolites and will be summarized by dose and treatment day. Concentrations of idronoxil obtained in the presence of doxorubicin will be compared to monotherapy.
 
Concentrations of doxorubicin and doxorubicinol will be determined after the administration of the infusion in the presence of NOX66 and will be compared to historical controls.
 
The relationship between PK parameters and AEs and other safety findings may be assessed by graphical methods and special summary tables.

	
Efficacy (Secondary analysis):
 
The DCR, ORR, and the incidences of CR, PR, SD, and Progressive Disease (PD) as assessed by RECIST v1.1 criteria will be summarized for the MTD of the combination by counts and percentages and exact 95% confidence intervals at the end of Cycles 2, 4, and 6, at the 6-month, 9-month, and 12-month follow-up visits and at End of Study.
 
Survival functions will be computed for OS and PFS by the Kaplan-Meier method. Estimates of median OS and median PFS will be presented.

	
Quality of Life (Secondary Analysis):
 
Quality of Life analyses will be performed for the FAS. Scale measures from the EORTC QLQ will be presented by dose for each visit, along with change from baseline to each visit. Brief pain inventory items and fatigue parameters will be summarized by dose at each visit as well as the change from baseline to each visit.

	
Exploratory Analysis:
 
An exploratory analysis will be performed to assess various factors which may contribute to response to the combination of NOX66 and doxorubicin. These factors include, NOX66 dose or exposure, cytokine, chemokine and ENOX2 response, lipidomic profiling (capturing over 300 lipid species as determined by liquid chromatography-tandem mass spectrometry), histopathology, and specific genetic mutations. The acceptability of the suppository dosage form by patients will also be determined.

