7.2 SECONDARY OBJECTIVES

- To determine single-and multiple-dose pharmacokinetics (PK) of idronoxil
- To determine the preliminary efficacy and quality of life (QOL) of the MTD of NOX66 in combination with doxorubicin.

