14 STATISTICAL SECTION

14.1 SAMPLE SIZE

Up to 18 patients may be enrolled in the Dose Escalation part of this study, in cohorts of 3 or 6 patients at each specified dose. Patients must take at least 80% of their prescribed doses to be considered eligible for MTD evaluation. Sixteen patients will be enrolled in the Dose Expansion part of this study.

These sample sizes are not based on statistical considerations but are deemed sufficient to determine the MTD for and to describe the pharmacokinetic characteristics of this agent.

An expansion cohort of N=16 will allow a total sample size of up to 34 patients. If the expected response rate is 18% (6/34) for a hypothetical comparator and the expected response rate of NOX66 will be 24% (8/34) in the current NOX66-004 trial, this sample size ensures an 85% probability that the observed response rate of NOX66- will be greater than 18%.

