14.2 ANALYSIS SETS

There will be two analysis sets

- Safety Set: All patients treated with at least one dose of idronoxil will be included in the Safety Set (SS). All analyses of safety, toxicity, and PK will be performed for this set.
- Full Analysis Set: All patients who complete at least one cycle of idronoxil + doxorubicin combination therapy will be included in the Full Analysis Set (FAS). Analyses of efficacy, tolerability, and biomarkers will be performed for this set.

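### Efficacy is an objective for the MTD, but the ORR tests, the PFS and OS curves and the 14.1 probability rest on patients at any NOX66 dose

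*Combined protocol and SAP*

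**What the plan says.** Section 7.2 states the efficacy objective as "To determine the preliminary efficacy and quality of life (QOL) of the MTD of NOX66 in combination with doxorubicin". The synopsis follows it for tumor response: DCR, ORR and the response categories "will be summarized for the MTD of the combination by counts and percentages", with exact 95% confidence intervals.

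The statistical section uses a different population. The synopsis defines the FAS as "All patients who completed at least one cycle of combination therapy (at any NOX66 dose"). Section 14.2 says of that set: "Analyses of efficacy, tolerability, and biomarkers will be performed for this set". Section 14.3.10 says "Treatment response will be assessed by RECIST v1.1 criteria for patients in the FAS". It then specifies a one-sided exact binomial test of ORR against 0.20 at about 0.025, at the end of Cycle 6 and again for best response, without naming any other set. For survival it says "The overall survival curve will be estimated for the FAS by the Kaplan-Meier method" and "The PFS curve will be estimated for the FAS by the Kaplan-Meier method".

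Section 14.1 says "An expansion cohort of N=16 will allow a total sample size of up to 34 patients". It writes the expected response rates as 6/34 for a hypothetical comparator and 8/34 for this trial, and claims an 85% probability of observing a rate above 18%.

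Two provisions pull toward the MTD. Section 14.3.1 has all data summarized by dose group and mentions a combined group only for safety. The synopsis allows separate summaries of the escalation and expansion parts.

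**The concern.** A hypothesis test needs one defined population. The objective points to the patients treated at the MTD. The analysis text, read literally, points to everyone who completed a combination cycle at 800, 1200 or 1800 mg. The two readings have different denominators and rejection boundaries, and if response depends on dose they estimate different quantities. A pooled test can miss an effect present at the MTD, or credit the MTD with one that came from other doses. Likewise, median PFS and OS from one any-dose curve would describe a mixture of doses, not the dose being carried forward.

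**Working it through.** **Inputs.** Escalation: up to 18 patients in cohorts of 3 or 6 (14.1). Expansion: 16, all at the MTD (8.1.2). Escalation patients at the MTD level: 6 (8.1.1, 8.3.1). Maximum total 34 (14.1); stated minimum about 28 (synopsis). Test: null 0.20, one-sided, about 0.025 (14.3.10). Expected ORR: 8/34 = 23.5%, written as 24% (14.1).

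**The plan's totals.** Maximum: 3 × 6 + 16 = 34. Minimum: 3 + 3 + 6 + 16 = 28. Both reproduce. The MTD-level group is 6 + 16 = 22.

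**Share of patients at other doses** = (total − 22) / total.

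| Escalation path | Total | Other doses | Share |
|---|---|---|---|
| All three levels filled to 6, MTD 1200 or 1800 mg | 34 | 12 | 35% |
| One lower level filled to 6, MTD 1800 mg | 31 | 9 | 29% |
| Stated minimum, MTD 1800 mg | 28 | 6 | 21% |
| MTD 800 mg, escalation stopped after 2 patients at 1200 mg | 24 | 2 | 8% |

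**Rejection boundaries.** With X ~ Binomial(n, 0.20), find the smallest r with P(X ≥ r) ≤ 0.025.

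- n = 22: P(X ≥ 9) = 0.020, while P(X ≥ 8) = 0.056. Reject at 9/22 (40.9%).
- n = 34: P(X ≥ 13) = 0.011. Reject at 13/34 (38.2%). At 12/34 (35.3%) the level is 0.027, which the word 'approximate' in 14.3.10 might allow.

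**Effect of mixing doses.** The rates are assumed for illustration, with 22 MTD patients and 12 others. The pooled count is the sum of two independent binomials.

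| True ORR at MTD | True ORR elsewhere | Pooled ORR | P(reject), MTD only (9/22) | P(reject), pooled (13/34) |
|---|---|---|---|---|
| 0.40 | 0.20 | (8.8 + 2.4)/34 = 0.329 | 0.55 | 0.31 |
| 0.20 | 0.40 | (4.4 + 4.8)/34 = 0.271 | 0.02 | 0.10 |
| 0.40 | 0.40 | 0.400 | 0.55 | 0.65 |

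In the second row the MTD rate equals the null, so the 0.10 is a false positive as far as the MTD is concerned.

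**The 85% in 14.1.** With X ~ Binomial(34, p):

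- P(X ≥ 6) = 0.845 at p = 8/34 and 0.859 at p = 0.24. This reproduces the 85%.
- But 6/34 = 17.6%, which is not above 18%. The smallest count above 18% is 7 (20.6%): P(X ≥ 7) = 0.720 at p = 8/34 and 0.741 at p = 0.24.
- For the MTD set, 4/22 = 18.2% is the smallest rate above 18%: P(X ≥ 4) = 0.796 at p = 8/34.

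**Precision.** Exact 95% intervals: 8/34 gives 11% to 41%; 5/22 gives 8% to 45%.

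**The case against.** A reader might infer that every efficacy result will be a mixture of doses, with a third of the response data coming from doses the objective does not ask about. The documents do not support that. The FAS defines who is included and does not by itself order pooling. Section 14.3.1 calls for summaries by dose group, and the synopsis reports ORR, DCR and the response categories for the MTD. Descriptive response at the MTD would therefore be visible. The third is also a maximum.

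A reader might also infer that the population could be chosen freely after the data are seen. Section 14.3.12 requires the SAP to be approved before the expansion cohort opens. Open-label escalation responses could be known by then, but none from the 16 expansion patients, who are most of the 22.

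Nor should 80% at n = 22 against 72% at n = 34 be read as a benefit of restricting to the MTD. The gap comes from the discreteness of the counts: the same calculation gives 66% at n = 23 and 82% at n = 33.

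It is also fair to say that efficacy is a preliminary, secondary aim of a Phase I study, that 14.1 says the sample sizes have no statistical basis, and that no design decision hangs on the ORR test. At the expected 8/34 the test rarely rejects under any rule: 5.3% at 9/22, 3.9% at 13/34, 8.3% at 12/34. Lower-dose responses also serve the exploratory dose-response objective.

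What remains is that no provision limits the ORR tests to the MTD, 14.3.10 expressly ties the survival curves to the FAS, and the dose-group rule in 14.3.1 assigns no population to a hypothesis test.

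**Conclusion.** The mismatch is real and narrow. It affects the two ORR tests, the Kaplan-Meier PFS and OS estimates and the probability in 14.1. It does not affect the descriptive ORR and DCR. Followed literally, 14.3.10 tests and estimates a group in which about 8% to 35% of patients received a dose other than the MTD. The boundary moves from 9/22 to 13/34 or 12/34. Under the assumed 40%/20% split, the chance of rejection falls from 0.55 to 0.31 with pooling at 13/34; under the reverse split it rises from 0.02 to 0.10. These probabilities depend on the assumed rates and on the 22 + 12 composition. Actual FAS counts may differ, because membership requires a completed combination cycle and patients may be replaced.

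Separately, the 85% in 14.1 is wrong at its own n = 34, whichever set is chosen. The probability of a rate above 18% is about 72% at a true 8/34, or 74% at a true 24%.

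This should be corrected before the analysis plan is fixed. It does not undermine the trial's primary safety and dose-finding aims.

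**What to change.** In 14.3.10, name the patients assigned to the MTD level (the escalation patients at that level plus the expansion cohort, about 22) as the set for both ORR tests and for the PFS and OS estimates. Present the any-dose FAS as supportive and by dose, which keeps the lower-dose data for the exploratory objective. State the rejection boundary for the planned n, so that 'approximate' leaves no choice. Align the synopsis and 14.1 with this set, and restate the 14.1 probability as about 80% at n = 22 for a true 8/34.

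The change is to wording only; dosing, enrollment and data collection stay as they are. The cost is precision and, if dose makes no difference, power: the interval goes from 11–41% (8/34) to 8–45% (5/22), and at a true ORR of 40% at all doses power is about 55% instead of 65% (13/34 rule).

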11.2.2 TREATMENT DISCONTINUATION

Patients will be discontinued from the study treatment if any of the following occurs as noted in Section [9.5](#).

- Disease progression based on RECISTv1.1
- An inter-concurrent illness that prevents further administration of NOX66
- An adverse event that is intolerable to continue the treatment with NOX66 and doxorubicin or any DLT (Section [8.3](#)) that has not resolved to Grade 1.
- Any other reason the Investigator considered that impacts the patient's safety.

For the patients who discontinue treatment, they will continue on study for follow-up visits for tumor evaluation. All anti-cancer treatments should be recorded in the eCRF. In those patients who have evidence of disease progression during the combination of NOX66 and doxorubicin, additional tumor evaluation assessments are not needed.

If a patient is withdrawn from the study at any time, either at his/her request or at the Investigator's discretion, regardless of the reason, the Investigator will record on the relevant page of the eCRF the reason(s) for withdrawal and the day of last dosing. The eCRF (and the clinical study report) will include reasons for patient withdrawals, as well as other details relevant to the patient's withdrawal.

Any patient who appears to be noncompliant from Cycles 2 to 6 should be counselled but not withdrawn from the study. Patients who discontinue for non-safety related reasons or for noncompliance prior to the end of Cycle 1 in the Dose-Escalation Part can be replaced.

Should any patient withdraw or be withdrawn from the study prior to the completion of the Month 18 follow-up visit, every effort should be made to complete the assessments at the End of Study (Section [11.6.2.12](#)). Patients experiencing adverse events should be followed until the AE has resolved, stabilized, or is no longer deemed clinically significant, as judged by the Investigator. Appropriate supportive and/or definitive therapy will be administered as required.

Discontinuation due to treatment failure, as defined by disease progression, is to be expected since doxorubicin is not curative for sarcoma and the optimal dose and dose frequency is not known for NOX66. Alternate treatments for sarcoma may be offered to the patient.

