14.3 STATISTICAL METHODOLOGY

14.3.1 GENERAL STATISTICS METHODS

All data will be summarized by idronoxil dose group. For safety analyses, a summary group consisting of all dose groups combined may also be presented.

For all measurements, the baseline value will be the last measurement taken before the first dose of study drug, whether idronoxil or of idronoxil + doxorubicin depending on the cohort.

Standard summary statistics will be presented for all measurements. For continuous variables, the standard summary statistics will be the number of observations (n), mean, standard deviation, median, minimum and maximum. For categorical variables, the standard summary statistics will be the number and percentage of observations in each category. Categories that are specified on the eCRF which contain no observations will be presented in the data summaries with a value of 0.

An AE with a completely missing start date will be assumed to start one minute after the date-time of the first idronoxil dose. If the severity of a reported AE is missing, it will be assumed that the event is severe; similarly, if the relationship of a reported AE to study treatment is missing, it will be assumed that the event is definitely related to treatment. No other missing data will be imputed. Incomplete start dates for Adverse Events and Concomitant Medications and incomplete end dates for AEs will have missing parts imputed by a conservative procedure which will be specified in the Statistical Analysis Plan (SAP).

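### The end-of-Cycle-6 response-rate test has no settled denominator for patients without a Cycle 6 scan, and its 20% null does not match the 18% benchmark in section 14.1

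*Combined protocol and SAP*

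**What the plan says.** Section 14.3.10 sets the population for response as the FAS and defines ORR as the relative frequency of patients with CR or PR. It summarises ORR and DCR visit by visit, at the end of Cycles 2, 4 and 6 and at follow-up visits to Month 18. It then adds a formal test: "At the assessment at the end of Cycle 6, a one-sided exact binomial test will be used to test the null hypothesis" that ORR is no greater than 20%, one-sided at about 0.025. A similar test against 20% follows for best response on study.

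Four other places bear on who is counted:

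- Sections 11.1.2.2 and 11.5.2 write ORR as (PR+CR)/All and DCR as (SD+PR+CR)/All. Neither says who All is at a given visit.
- Section 14.3.1 gives a general rule: "For categorical variables, the standard summary statistics will be the number and percentage of observations in each category". After its rules for adverse events it adds: "No other missing data will be imputed".
- Section 11.2.2 says: "In those patients who have evidence of disease progression during the combination of NOX66 and doxorubicin, additional tumor evaluation assessments are not needed".
- Sections 11.6.2.9 and 11.6.2.12 and note 15 to Table 4 provide Early Termination scans.

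On the benchmark, section 14.1 argues from a different rate: "If the expected response rate is 18% (6/34) for a hypothetical comparator", with 24% (8/34) expected for NOX66 and an 85% probability of observing more than 18%. The same section says the sample sizes do not rest on statistical considerations.

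**The concern.** A patient found to have progressed at the Cycle 2 or Cycle 4 scan stops treatment (section 9.5), may not start another cycle (Table 4, note 2) and needs no further tumour assessment. That patient may have no Cycle 6 record. If percentages are taken over observations and nothing is imputed, the patient leaves the Cycle 6 denominator. Those who leave are mostly non-responders, so the rate rises and the test can reject when the combination adds nothing. Visit-wise DCR has the same weakness, and later visits have more patients to lose.

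The second issue is the reference rate. Section 14.1 judges the response rate against 18%, section 14.3.10 tests it against 20%, and neither gives a reason. With 22 patients, 4 responses (18.2%) would be above one and below the other. A reader may also take the 85% in section 14.1 as the strength of the planned test, which it is not.

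**Working it through.** **Inputs.** Null 0.20, one-sided 0.025 (14.3.10). Benchmark 18%, expected rate 24% or 8/34, N up to 34 (14.1). N=22 is the case of 6 escalation patients at the MTD plus 16 in expansion, because the synopsis summarises efficacy for the MTD. Median PFS values of 4.1, 4.6, 6.6 and 7.4 months are quoted in section 6.1 for other trials. The documents give no attrition figure, so attrition is an assumption. All treated patients are assumed to be in the FAS.

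**1. The plan's 85%.** P(X ≥ 6 | 34, 0.24) = 0.859, and 0.845 at 8/34. The figure reproduces if 6/34 = 17.6% counts as reaching the mark. Strictly above 18% needs 7/34, which gives 0.741 and 0.720.

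**2. The planned test with all patients counted.** Take the smallest c with P(X ≥ c | N, null) ≤ 0.025.

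| N | Null | c | Exact level | Rejects at 24% | Rejects at 8/34 |
|---|---|---|---|---|---|
| 34 | 20% | 13 | 1.09% | 4.6% | 3.9% |
| 34 | 18% | 12 | 1.24% | 9.3% | 8.3% |
| 22 | 20% | 9 | 2.01% | 6.0% | 5.3% |
| 22 | 18% | 9 | 1.02% | 6.0% | 5.3% |

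The level is called approximate. If that were taken to allow 12/34 against 20%, the level would be 2.7% and rejection at 24% would be 9.3%.

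**3. How much the denominator matters.** Take 8 responders, all scanned at Cycle 6, and test against 20%:

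| Counted | 34 | 28 | 24 | 20 | 19 | 18 |
|---|---|---|---|---|---|---|
| p | 0.367 | 0.182 | 0.089 | 0.032 | 0.023 | 0.016 |

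The same 8 responses are unremarkable over 34 patients and pass the threshold over 19.

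**4. Rejection rate when the true ORR is 20%, scanned patients only.** A patient is lost if progression has occurred by the Cycle 4 scan, day 4 × 21 = 84, or 84/30.44 = 2.76 months. With exponential PFS, the share still scanned is S = 0.5^(2.76/median). All responders are assumed still scanned, so a scanned patient is a responder with probability 0.20/S. The rejection rate is the sum over m of P(m scanned | N, S) × P(X ≥ c(m) | m, 0.20/S), where c(m) is the exact critical value for m.

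| Median PFS (months) | S | Scanned-only ORR | Rejects, N=34 | Rejects, N=22 | Rejects, N=34, 20% of responders also lost |
|---|---|---|---|---|---|
| 4.1 | 0.627 | 31.9% | 20.1% | 12% | 8.8% |
| 4.6 | 0.660 | 30.3% | 16.6% | 10.4% | 6.9% |
| 6.6 | 0.748 | 26.7% | 9.7% | 6.5% | 3.4% |
| 7.4 | 0.772 | 25.9% | 8.3% | 5.8% | 2.8% |

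At N=22 with 20% of responders lost, the range is 2.2-5.8%.

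**The case against.** The strongest defence is that the endpoint definition is specific and the percentage rule in 14.3.1 is general. ORR is written over All, the population is the FAS, and 14.3.10 speaks of the frequency of patients, not of observations. Counting every FAS patient needs no imputed scan. This stands in part: a reader might infer that the scanned-only denominator is the plan's rule, and the documents do not support that. They support only that the denominator is unsettled, because All is undefined and an unassessed patient is never classified.

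A reader might also infer that progressors are never scanned again. Section 11.2.2 says only that scans are not needed. Section 11.6.2.12 asks for a scan that includes patients who leave the study for progression, and the Cycle 6 Day 21 column of Table 4 doubles as Early Termination. However, note 15 applies to those who leave the study, section 11.2.2 keeps patients who stop treatment on study, and no text carries an Early Termination scan or an earlier PD into the Cycle 6 analysis.

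Taking PFS to day 126 would give a larger effect, 15-39% at N=34. That is not justified: progression first seen on the Cycle 6 scan is an observed PD and stays in the denominator on either reading.

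This is not the only formal efficacy test. The best-response test is less affected, since a patient with PD at Cycle 2 has an observed best response.

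Finally, section 14.3.12 defers data-handling rules to an SAP approved before the expansion cohort opens. That is a proper place for the rule. But the study is open-label, so responses from up to 18 escalation patients could be visible by then.

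**Conclusion.** The denominator for the Cycle 6 ORR test, and for visit-wise ORR and DCR, is inconsistent across sections 11.1.2.2, 11.2.2, 11.5.2, 14.3.1 and 14.3.10. On the scanned-only reading the test is anti-conservative: about 8-20% rejection at N=34 and 6-12% at N=22 when the true ORR is 20%. Those figures assume exponential PFS with medians of 4.1-7.4 months, loss by the Cycle 4 scan and every responder still scanned. Loss of 20% of responders brings N=34 down to about 3-9%. With all 34 counted the level is 1.1%.

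The 18% and 20% benchmarks also disagree. It would be wrong to infer that the trial is sized against 18%: section 14.1 disclaims a statistical basis, and 18% is only the mark in its probability statement. Nor is a power claim broken, since none is made for this test. What holds is that the 85% describes a different criterion, while the test itself needs 13/34 and rejects in 4-5% of trials at 24% (8-9% against 18%).

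This should be fixed but does not block the trial. Efficacy is a secondary objective in a Phase I study, and no decision is tied to the test.

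**What to change.** - In 14.3.10, state that at every visit the denominator for ORR and DCR is all FAS patients, and that prior PD, death, being off study or having no scan counts as neither response nor disease control.
- Use one reference rate in 14.1 and 14.3.10, with the reason for it.
- In 14.1, give the test's chance of rejecting at 24% beside the 85%, and say that the two are different quantities.
- State whether the test covers all doses (up to 34) or the MTD only, as the synopsis summary does.

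Replacing the test with the exact 95% confidence intervals already in the synopsis is an option, but a matter of preference. The cost is wording only, with no new data collection. Reported Cycle 6 and later rates will look less favourable than on a scanned-only count. The rule is best fixed before escalation responses are known.

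### The 85% response figure in 14.1 neither matches its own wording nor describes the exact test in 14.3.10, whose power at the expected 24% is about 4–9% with 34 patients

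*Combined protocol and SAP*

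**What the plan says.** Section 14.1 (Sample Size) first states that "These sample sizes are not based on statistical considerations". It then adds a response argument. The size is set out as "An expansion cohort of N=16 will allow a total sample size of up to 34 patients". The benchmark is introduced with "If the expected response rate is 18% (6/34) for a hypothetical comparator", and the assumption for the combination is that "the expected response rate of NOX66 will be 24% (8/34) in the current NOX66-004 trial". From these it concludes that "this sample size ensures an 85% probability that the observed response rate of NOX66- will be greater than 18"%.

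Section 14.3.10 (Efficacy Analyses) sets a different criterion: "a one-sided exact binomial test will be used to test the null hypothesis that the ORR is no greater than 0.20 (20"%). The test looks for a higher rate, its level is approximately 0.025, and its timing is the assessment after Cycle 6. The section continues: "A similar test against the performance level of 0.20 will be performed for the rate of best objective response on study". Neither section gives a critical number of responders, an actual size or a power for these tests.

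The analysed set is not settled. Section 14.3.10 assesses response in the Full Analysis Set, which 14.2 defines as all patients completing at least one combination cycle; the synopsis adds that this is at any NOX66 dose. The synopsis efficacy paragraph, however, summarises response for the MTD of the combination, with exact 95% confidence intervals, and mentions no test.

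**The concern.** The two sections use different benchmarks (18% and 20%) and different kinds of rule. One asks whether a point estimate clears a line, with no error control. The other is a significance test at a set level. A high probability for the first says nothing about the second.

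If the combination delivers the rate that 14.1 expects, the two tests in 14.3.10 will most likely be non-significant. Someone who has seen only the 85% has no warning of this and could misread the result as evidence that the combination is inactive. Separately, the 85% cannot be reproduced from the sentence as printed.

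**Working it through.** **Inputs.** From 14.1: N = 34 (18 escalation + 16 expansion), expected rate 24% (8/34 = 23.53%), comparator 18% (6/34 = 17.65%), stated probability 85%. From 14.3.10: null rate 0.20, one-sided, level about 0.025. Other possible N: 28 (the synopsis's expected number if escalation uses the minimum), 22 (6 + 16 at the MTD), 16 (expansion alone).

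**Formula.** X ~ Binomial(N, p), and P(X ≥ r) = Σ C(N,k) p^k (1−p)^(N−k) for k = r to N.

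**Step 1: reproduce the 85%.** N = 34.

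| Event | Observed rate | p = 8/34 | p = 0.24 |
|---|---|---|---|
| X ≥ 6 | 17.65% | 84.5% | 85.9% |
| X ≥ 7 | 20.6% | 72.0% | 74.1% |

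The 85% is therefore the chance of at least 6/34. But 6/34 is below 18%, so a rate strictly greater than 18% needs 7/34, and the probability is 72–74%.

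**Step 2: error control of that rule.** At a true rate of 18%, P(X ≥ 7) = 41.4%, so the criterion as worded is met about two times in five when the combination is no better than the comparator. Counting 6/34 as a pass raises this to P(X ≥ 6) = 59.1%.

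**Step 3: the test in 14.3.10.** The strict critical count is the smallest r with P(X ≥ r | 0.20) ≤ 0.025. Because the level is described as approximate, the next count down is shown too. Power is P(X ≥ r) at p = 8/34 and p = 0.24.

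| N | Reject at | Observed rate | Actual size | Power at 8/34 | Power at 24% |
|---|---|---|---|---|---|
| 34 | ≥ 13 | 38.2% | 1.1% | 3.9% | 4.6% |
| 34 | ≥ 12 | 35.3% | 2.7% | 8.3% | 9.3% |
| 28 | ≥ 11 | 39.3% | 1.5% | 4.6% | 5.2% |
| 28 | ≥ 10 | 35.7% | 3.9% | 10.1% | 11.2% |
| 22 | ≥ 9 | 40.9% | 2.0% | 5.3% | 6.0% |
| 16 | ≥ 8 | 50.0% | 0.7% | 1.9% | 2.1% |
| 16 | ≥ 7 | 43.8% | 2.7% | 6.0% | 6.6% |

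The looser count at N = 22 (8 responders) has size 5.6%, more than twice the stated level, and is not treated as a reading of it.

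**Step 4: what the test can detect.** At N = 34, power is 64.6% (13 responders) or 76.7% (12) at a true rate of 40%, and 83.3% or 90.6% at 45%. Solving P(X ≥ r) = 0.80 gives a true rate of about 44% (13) or 41% (12).

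**Step 5: the confidence interval.** The exact (Clopper-Pearson) 95% lower limit is 0.222 at 13/34 and 0.197 at 12/34. It exceeds 0.20 exactly when the strict test rejects.

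**The case against.** A reader might infer that the protocol presents 85% as the power of its response analysis, and that a false negative is built into the design. The documents do not support either reading. Section 14.1 disclaims a statistical basis for the sample sizes, describes its 85% as a probability about the observed rate, and mentions no test, level or power. No section names 24% as the alternative for the 0.20 test; in 14.1 it is set against a hypothetical 18% comparator.

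Nor does a trial decision hang on the test. The primary objectives are the MTD and safety, and efficacy is secondary and preliminary. The recommended Phase 2 dose rests on DLTs and acceptability, and the interim results will not modify or stop the study. Low power for a four-point difference is unsurprising in a Phase I trial of this size, and Step 4 shows that the test can detect a large effect.

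An exact 95% interval for response is already planned, and Step 5 shows that its lower limit carries the same verdict as the strict test. Moving to the interval changes how the result is read, not the information in it. Section 14.3.12 also defers further detail to a separate SAP, which is not among the documents.

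These points limit the concern to what the text states and omits. They do not repair the mismatch between the 85% and its wording, or supply the missing properties of a test that the protocol specifies.

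**Conclusion.** The concern holds in this limited form. The 85% corresponds to at least 6/34 responders (84.5–85.9%), not to the event described, for which the figure is 72–74%. It also does not describe the test in 14.3.10. With 34 patients and a true rate of 8/34 to 24%, that test rejects 3.9–4.6% of the time at 13 responders or 8.3–9.3% at 12, so a non-significant result is expected in about 91–96% of such trials. For N of 16 to 28 the power is about 2–11%.

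The figures assume independent patients with a common response rate, one binary response per patient, and that every patient in the stated N is counted. The range reflects two things the documents leave open: which set is analysed, and how far the approximate level may exceed 0.025. It would be wrong to say that power is below 10% on every reading, because 28 patients with a cut-off of 10 gives 10.1–11.2%, at a size of 3.9%. No reading comes near 85%.

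**What to change.** In 14.1, replace the 85% sentence with the properties of the planned test: the analysed N, the critical count, the actual size, the power at 24%, and the true rate giving 80% power (about 41–44% at N = 34). Choosing N means first reconciling the Full Analysis Set at any dose (14.3.10, with the synopsis definition) with the MTD-only summary in the synopsis efficacy paragraph. If the observed-rate statement is kept, either restate the event as at least 6/34 or change the figure to 72–74%.

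In 14.3.10, state that the response rate is interpreted by estimation with its exact 95% confidence interval, and that non-rejection at 0.20 is not evidence against a true rate of 24%. Apply the same wording to the best-response test.

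The cost is protocol and SAP wording only, with no extra patients or procedures. The downside is that the printed figure becomes much less favourable. Section 14.3.12 requires the SAP to be approved before the Dose Expansion Cohort opens, which is a natural point to make the change.
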